8.1.3 Blood sample collection

The nurse or clinical officer in the field team will obtain 2ml of whole blood from participants. This will happen while the study team is still in the participant's homestead. Blood will be collected in a tube containing Ethylenediaminetetraacetic acid (EDTA) using the aseptic technique, placed in a sample

transportation box at +4 to +8°C for shipment to the central Malaria Drug Resistance Laboratory (MDR) for the gametocyte detection assays by PCR. Blood sample collection will conclude the field visit. All study documents that will be filled out while in the field will be transported back to the KCRC. A signed copy of the ICF will be given to the study participant. The blood samples will be batched and transported to the MDR, to arrive within 6 hours of collection. In the event that the field team anticipates that the 6 hour window to ship the blood samples to MDR is closing in, the team will contact the transport dispatcher at the KCRC to pick up the sample transportation box from the field.

8.1.4 Enrolment of gametocytemic participants

Participants who are found to harbor gametocytes as per the PCR test (with a cT value of less than 31) will be enrolled to participate in the mosquito feeding assays. The MDR expects to turn around the results of the PCR tests within approximately 48 hours of sample collection. The results of the tests will be communicated to the study team in Kombewa, who will then contact the participants. For participants who do not have gametocytes detected, they will be informed of the results and the study team will explain to them that their participation has ended. Participants who are gametocytemic will be invited to participate in the mosquito feeding assays. Participants who are found to have very low density gametocytemia (PCR cT value of 31 and above) will not be invited to participate in mosquito feeding assays. They will, however, be offered treatment to clear their parasitemia as described in section 7 of this protocol. The team in Kombewa will facilitate the movement of the participants from their homesteads to the KEMRI/USAMRD-A facilities where the feeding assays will take place as described in section 8.1.5.

8.1.5 Mosquito feeding assays (DSFA & DMFA)

Mosquito feeding assays involve feeding unfed, sterile (pathogen-free), insectary-reared *Anopheles gambiae* mosquitoes on malaria infected humans for the purposes of obtaining oocyst and sporozoite counts in mosquito's midgut and salivary glands, respectively, thereby allowing an accurate evaluation of malaria transmission. The KEMRI/USAMRD-A/K entomology laboratory maintains a colony of *An. gambiae sensu stricto* (KISUMU strain) that were originally collected at Lwanda village, Siaya County in western Kenya. Mosquitoes are provided a 10% water infused sucrose meal daily, maintained at 30°C (70-80% relative humidity), and reared under very stringent conditions. Cow's blood is used to maintain the colony, and only the progeny (3-5 day old female mosquitoes) are used for the feeding assays. Additionally, 10% of each new generation of mosquitoes are pooled and tested for arboviruses. This study will conduct two types of mosquito feeding assays using study participants concurrently: Direct Skin Feeding Assay (DSFA) and Direct Membrane Feeding Assay (DMFA).

DMFA will be performed using the general procedures of Bousema et al. and DA et al. (13,14) for membrane feeding, with the notable exception that serum in collected subject blood samples will not be replaced with non-immune serum. Briefly, 0.12 mL of whole blood collected from study participants just prior to the feeding assays will be transferred to 2ml-capacity glass receptacles that comprise the artificial feeders warmed at 36-37 °C using a circulating water bath and provided to 3-5-day old starved female *An. gambiae sensu stricto* mosquitoes (KISUMU strain; n= 30 per cup; 2 cups per subject).

DSFA will be performed using the protocol described by Bonnet et al. and Bousema et al. (11,12) (studies successfully completed in Sub-Saharan Africa). Sixty sterile 3-5-day old *An. gambiae sensu*

stricto female mosquitoes (KISUMU strain) will be starved for five hours and transferred to a cardboard cup covered with netting prior to use. The mosquito containing cup will be placed on the calf or arm of each volunteer to feed for 15 minutes, after which antihistamine ointment will be applied to the volunteer's skin. (KISUMU strain; n=60 per cup; 1 cup per subject).

Day 1 procedures: Consenting human subjects identified as gametocytemic by RT-PCR will be transported to the KEMRI/USAMRD-A/K laboratory in Kisian within 48 hours of being identified in order to participate in the mosquito feeding assay. A blood sample (~ 1 mL) for DMFA will be collected from each subject (Table 2) prior to the DSFA. A blood sample (~ 5 mL) for serum collection will be collected and a membrane feeding assay may be performed (risk mitigation) only if gametocyte-positive subject fails to transmit any parasites to any mosquito in either the DSFA or DMFA on days 1 or day 2. Sera will be destroyed before study close-out. Upon completion of the first DSFA, the subjects will stay overnight under the supervision of KCRC staff at KCRC-affiliated district hospital. Subjects will not return to their home at the end of day 1 procedures.

[figure not shown]
Day 2 procedures: Subjects will be transported to the KEMRI/USAMRD-A/K laboratory in Kisian for the second DMFA and DSFA assay within +/- 3 hours of the time when the first DSFA was performed. The two sequential mosquito feeding DSFA and DMFA assays on day 1 and day 2) will be performed in all study participants within 24 hours (+/- 3 hours) to mimic a potential follow-on study design proposed to evaluate infectiousness of individuals before and after the administration of transmission-blocking intervention (drug and/or monoclonal antibody). A different skin site will be selected for DSFA on Day 2. The remainder of the blood sample collected for DMFA will be used to prepare malaria blood films (MBFs). Dried blood spots (DBS) for RT-PCR for *Plasmodium* detection will be collected and stored for a maximum of 30 days as a back-up diagnostic assay and then destroyed. There will be no future use archiving of biological samples.

Upon completion of day 2 of DSFA, subject will take day 1 of both Primaquine and Coartem anti-malarials. Coartem tablets for days 2 and 3 will be provided to subjects per standard operating procedures. Upon release from the clinic, the participation of each subject will be ended.

Mosquito and insectary procedures: All fed (and potentially infectious) mosquitoes will be held in locked environmental chambers located at the ACL-2 insectary at the USAMRD-A/K entomology facilities for security and optimum developmental conditions. Any unfed mosquitoes will be transferred to a second container and killed by placing in a -20°C freezer for 48 hours prior to disposal.

Out of the 60 mosquitoes in each cup, it is estimated that approximately 5% will not feed. Therefore 29 will be held up to Day 9 or Day 10 post feed for oocyst count determination and the remaining 28 will be held up to Day 14 or Day 15 post feed for sporozoite count determination. The maximum anticipated mortality for mosquitoes held to D9/D10 is approximately 15%, while for those held to D14/D15 is approximately 50%. Thus, at least 25 mosquitoes will be available for oocyst counts and at least 15 for sporozoite counts as described in section 8.1.9.3 below. This is summarized in the figure below.

Figure 8: Disposition of mosquitoes after the feeding assays

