3.3.1.5 Risks of Receipt of Artemether/Lumefantrine (Coartem®)

Adult subjects who receive Coartem® may experience the following adverse events:

Metabolism and nutrition disorders

Very common: Decreased appetite

Psychiatric disorders

Very common: Sleep disorder

Nervous system disorders

Very common: Headache, dizziness

Common: Clonus

Uncommon: Somnolence, hypoesthesia, ataxia

Cardiac disorders

Very common: Palpitations

Respiratory, thoracic and mediastinal disorders

Common: Cough

Gastrointestinal disorders

Very common: Vomiting, abdominal pain, nausea

Common: Diarrhea

Skin and subcutaneous tissue disorders

Common: Rash, pruritus

Uncommon: Urticaria

Musculoskeletal and connective tissue disorders

Very common: Arthralgia, myalgia

General disorders and administration site conditions

Very common: Asthenia, fatigue

Uncommon: Gait disturbance

Investigations

Uncommon: Electrocardiogram QT prolonged, liver function tests increased

Symptoms are generally mild and self-limited without any treatment required. To ensure compliance, subjects will receive the first dose of Coartem® under the supervision of a medical provider at the CRC and sent home with the remaining doses and instructions on how to complete the course. The management of any persistent side effects is usually symptomatic.

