7.1.3 Dosing and Administration

Refer to dosing and administration of Coartem® and primaquine in Table 1. The dosage for Coartem® and primaquine are as per the manufacturer's package insert. Coartem® is part of the usual treatment prescribed for malaria as per the Kenya standards of treatment for malaria. The addition of primaquine is not part of standard of care, however the participant will benefit from the reduction of gametocyte carriage as a result of primaquine administration. The administration of Primaquine and the first dose of Coartem will be done under direct observation by clinic staff. According to standard of care in Kenya for malaria treatment, doses of Coartem on days 2 and 3 will be taken by the subject as instructed by study staff. The KCRC Pharmacy will maintain accountability logs for dispensed drugs.

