7.1.4 Justification for treatment of asymptomatic parasite carriers

Plasmodium spp. asymptomatic carriers, defined as individuals with detectable asexual or sexual parasites in their blood and an absence of any acute clinical symptoms of malaria, asymptomatic carriers are not yet targeted by national malaria intervention strategies in many malaria-endemic countries, including Kenya. Local malaria treatment guidelines are currently focused on the management of symptomatic malaria: the starting point for treatment algorithms is symptoms such as fever, with an emphasis on testing for malaria prior to treatment. Asymptomatic carriers do not seek treatment for their infection. They and, therefore, constitute a reservoir of parasites for maintaining the parasite life cycle and transmission by the anopheline vector and thus a real public-health risk. Studies have suggested that a proportion of individuals with asymptomatic blood-stage malaria infection may eventually become symptomatic, although reinfections or other causes of fever cannot always be ruled out. These asymptomatic parasites have also been linked with chronic anemia and co-infections with invasive bacteria. As such, the treatment of asymptomatic malaria carriers who will be identified in this study will have both individual and public health benefits. At the individual level, parasite clearance may reduce the risk of getting symptomatic malaria later on and may also reduce the risk of adverse health outcomes associated with parasite carriage, such as chronic anemia and co-infections with invasive bacteria. From a public health point of view, clearance of parasitemia may reduce the risk of malaria transmission to others, especially to other members of the household, some of whom may be susceptible to severe malaria. Good clinical judgment strongly encourages that persons who are asymptomatic and infected with malaria parasites when found to be positive by molecular diagnostic techniques be provided antimalarial medications to clear both the asexual parasites and sexual stage gametocytes.

Table 1. Anti-malarial Medications

Study Agents	Dosage forms and strength	Body weight	Day 1**** (AM)	Day 1 (+8hr)	Day 2 (AM)	Day 2 (PM)	Day 3 (AM)	Day 3 (PM)
COARTEM *	artemether (20 mg) and lumefantrine (120 mg)**	> 35 kg	4 tabs	4 tabs @ 8 hrs.	4 tabs	4 tabs	4 tabs	4 tabs
PRIMAQUINE***	primaquine phosphate tablets 26.3 mg primaquine phosphate (equivalent to 15 mg primaquine base)	> 35 kg	1 tab	-	-	-	-	-

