* Coartem should be taken with food

** Coartem is also available as artemether (80mg) and lumefantrine (480mg) tablet for adults. The dosage of this strength is 1 tablet at each dosing time point.

***Primaquine may be taken with food

**** Refers to first day of drug taken after 2nd DSFA

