8. STUDY PROCEDURES

8.1 Study procedures and evaluations

Table 2. Time and event

Procedures	Visit Day -1 to 0 (Screening)	Visit Day 1 (Baseline/Enrollment)	Visit Day 2 (Final)
Window (hours)	—	—	+/-3
Obtain informed consent of potential participant	●		
Obtain demographic information	●		
Obtain medical history	●		
Obtain medications history	●		
Perform medical examinations	●	●	●
Collect blood for gametocyte detection tests (2 mL) by PCR	●		
In females, urine pregnancy test	●		●
Verify inclusion/exclusion criteria	●	●	●
Verify gametocyte detection (RT-PCR) test results		●	
Record vital signs	●	●	●
Blood sample for serology – 5 mL*		●	
Blood sample for DMFA and microscopy (1ml)		●	●
DSFA		●	●
Admit the study participant for observation overnight		●	
Record local and unsolicited AEs as reported by participant or observed by investigator before DSFA and 30 minutes after DSFA		●	●
Administer low dose primaquine* and first dose of Coartem® and give remaining Coartem® dose with instructions			●

- Sera collected will be assayed in membrane feeding assay (risk mitigation) only if gametocyte-positive subject fails to transmit any parasites to mosquitoes in either the DSFA or DMFA performed either on day 1 or day 2. Sera will be destroyed before study close-out.

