8.1.6 Management of study participants

Subjects found to harbor gametocytes will be admitted for a period of approximately 24 hours to an observation ward at the Kombewa CRC or the Kombewa sub-county hospital located across the street from the CRC while awaiting their second feed as described above. While in the ward, they will be encouraged to dress in clothing that covers most of the skin so as to minimize contact with mosquitoes. In order to allow for the successful execution of the mosquito feeding assays, all gametocytic participants will be offered antimalarial treatment only after completion of all feeding assays. A full course of artemether/lumefantrine 480/80mg (Coartem®) along with a single low dose of primaquine (15 mg primaquine base) will be administered as per the package insert – primaquine and the first dose of Coartem® will be witnessed by study staff. Primaquine will not be given to pregnant or breastfeeding women. Given that PCR testing tends to detect parasite levels much lower than the detection limit of standard clinical tests for malaria (RDT and microscopy), standard clinical testing will not be performed prior to administration of antimalarial treatment to clear parasitemia. Administration of primaquine to malaria patients is not part of standard care in Kenya. Primaquine, however, is specifically effective against gametocytes and therefore serves the purpose of ensuring clearance of circulating gametocytes in the participant. The administration of antimalarials to asymptomatic individuals is currently not part of standard of care in Kenya.

Gametocytic participants who show signs of malaria while under observation will be managed in accordance to the Kenya MoH National Guidelines for the Diagnosis, Treatment and Prevention of Malaria. Such participants will not participate in further feeding assays and will be replaced until the desired sample size is achieved.

Study participants who withdraw consent while under observation and are still asymptomatic will be offered antimalarial treatment to clear parasitemia as described above prior to leaving the observation

ward. If they are symptomatic, they will be offered the choice to be managed by the study clinical team in accordance to the Kenya MoH National Guidelines for the Diagnosis, Treatment and Prevention of Malaria, or be referred to the Kenya Ministry of Health clinician for further management.

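### The Coartem instructions conflict on which of the six doses go home, leave the Day 1 +8 h dose unassigned in 7.1.3, and, separately, state the strength in reverse order in 8.1.6

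*Protocol*

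**What the plan says.** Table 1 (Protocol, printed under 7.1.4) lists Coartem at six dosing points: morning and +8 h on Day 1, then morning and evening on Days 2 and 3. Each is 4 tablets of 20 mg artemether and 120 mg lumefantrine. A footnote adds that "Coartem is also available as artemether (80mg) and lumefantrine (480mg) tablet for adults", taken as 1 tablet per dosing point. Another footnote defines Day 1: "Refers to first day of drug taken after 2nd DSFA". Drug Day 1 therefore falls on study Day 2.

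Who takes or receives what is stated in five other places:

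- **3.3.1.5:** the first dose is supervised at the research center and the participant is "sent home with the remaining doses and instructions on how to complete the course".
- **Table 2 (8.1), final visit:** staff administer primaquine and the "first dose of Coartem® and give remaining Coartem® dose with instructions".
- **7.1.3:** the reader is referred to Table 1 for dosing. Primaquine and the first Coartem dose are directly observed, and "doses of Coartem on days 2 and 3 will be taken by the subject as instructed by study staff".
- **8.1.5, Day 2 procedures:** after the second skin feed the participant takes drug Day 1 of both medicines. Then "Coartem tablets for days 2 and 3 will be provided to subjects per standard operating procedures", and participation ends on release.
- **8.1.6:** "A full course of artemether/lumefantrine 480/80mg (Coartem®) along with a single low dose of primaquine" is given according to the package insert, with primaquine and the first Coartem dose witnessed.

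**The concern.** There are two independent problems.

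The first is supply and responsibility. Two places send home everything after the first dose, and a third sends home days 2 and 3 only. The difference is exactly the Day 1 +8 h dose. Section 7.1.3 puts that dose neither among those observed nor among those the participant takes.

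The second is the strength in 8.1.6, whose two figures stand in the opposite order to the Table 1 footnote although the components are named in the same order.

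These antimalarials are the only medicines used in the study (section 7), and clearing the infection is listed as a benefit to participants (3.3.2). Section 8.1.7 points to 8.1.5 for treatment, so the 8.1.5 sentence is operative text. Participants with a cT of 31 or above are treated under section 7 instead (8.1.4), where 7.1.3 leaves the gap. Staff combining 7.1.3 with 8.1.5 could send someone home one dose short, with no later visit at which it would be noticed. The pharmacy logs required by 7.1.3 would also have two possible take-home counts to be checked against.

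**Working it through.** **Table 1 course.** 2 dosing points × 3 days = 6. At 4 tablets each, 6 × 4 = 24 tablets of 20/120 mg, or 6 × 1 = 6 tablets of 80/480 mg. Table 1 sets amounts and times. It does not say where doses are taken or how many go home.

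**Dosing points by place and reading**

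| Place | In clinic | Taken or supplied for home | Accounted for |
|---|---|---|---|
| 3.3.1.5 | 1 | 6 − 1 = 5 | 6 |
| Table 2 | 1 | 6 − 1 = 5 | 6 |
| 7.1.3 | 1 observed | 2 × 2 = 4 | 5; +8 h not assigned |
| 8.1.5, drug Day 1 meaning both Table 1 doses | 2 | 2 × 2 = 4 | 6 |
| 8.1.5 supply with the first-dose wording of 7.1.3 and 8.1.6 | 1 | 2 × 2 = 4 | 5; +8 h not assigned |
| 8.1.6 | 1 witnessed | count not given | full course stated |

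The Table 2 row assumes that its remaining dose, written in the singular, means the rest of the course.

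**Take-home supply**

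- 3.3.1.5 and Table 2: 5 × 4 = 20 tablets of 20/120 mg, or 5 of 80/480 mg.
- 8.1.5: 4 × 4 = 16 tablets of 20/120 mg, or 4 of 80/480 mg.
- Difference: 20 − 16 = 4 tablets (or 1), one dosing point, 1/6 = 16.7% of the course.

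**Is the participant still in clinic at +8 h?** The 8.1.5 reading that reaches six needs both Day 1 doses to be taken before release. Table 2 marks overnight admission for Visit Day 1 only, which is before treatment. The only observation period stated after a skin feed is 30 minutes (3.3.1.3, Table 2). No 8-hour stay after the first Coartem dose is scheduled.

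**Strength**

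- Table 1: 4 × 20 = 80 mg artemether and 4 × 120 = 480 mg lumefantrine, which equals the footnote's single 80/480 mg tablet. The table and its footnote agree.
- 8.1.6 as written, artemether/lumefantrine 480/80: 480 ÷ 80 = 6 times the Table 1 artemether per dosing point, and 80 ÷ 480 = 1/6 of its lumefantrine.
- As a course total it fails too: 24 × 20 = 480 mg artemether matches the first figure, but 24 × 120 = 2,880 mg lumefantrine does not match 80.

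**The case against.** A reader might infer that following 8.1.5 by itself drops the 8-hour dose. The text does not support that. The sentence before the quoted one has the participant take drug Day 1 of Coartem, which in Table 1 is two doses, and 2 + 4 = 6. The dose falls out only under 7.1.3, or when the 8.1.5 supply is joined to the first-dose wording elsewhere and release comes before 8 hours. What remains against 8.1.5 is that it is ambiguous: it pairs drug Day 1 of Coartem with single-dose primaquine, both taken when the feed is completed, and it provides no stay for a second dose.

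It is also fair to say that 7.1.3 sends the reader to Table 1, that 8.1.6 requires a full course, that the Table 1 footnote separates drug days from study days, and that 8.1.5 defers to standard operating procedures not shown here. Practice at the site may therefore be clear. None of this removes the difference between 3.3.1.5 with Table 2 and 8.1.5, or assigns the +8 h dose in 7.1.3.

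On strength, a reader might infer a sixfold artemether exposure. The documents do not show one. No product described in the protocol has a 480/80 strength, 8.1.6 defers to the package insert, and the figure looks like a transposition in one line. It is still a contradiction with Table 1. It also has no bearing on the 8-hour dose, so neither problem explains the other.

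**Conclusion.** The point holds as two separate inconsistencies in treatment instructions.

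1. The take-home counts differ by one dosing point (20 versus 16 tablets of 20/120 mg, or 5 versus 4 of 80/480 mg), and 7.1.3 does not assign the +8 h dose. The 16.7% is a share of tablets supplied. It is not a shown loss of treatment, and it should not be applied to every treated participant, because those with a cT of 31 or above are treated under section 7 and not under 8.1.5.
2. The strength in 8.1.6 is the reverse of the Table 1 footnote.

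The counts rest on Table 1's six dosing points and on reading the remaining doses in 3.3.1.5 and Table 2 as everything after the first. Because treatment follows the last feed, endpoints, sample size and analysis are untouched. The matter is one of participant care and drug accountability, and it should be corrected.

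**What to change.** Reconcile 3.3.1.5, 7.1.3, 8.1.5, 8.1.6, Table 1 and Table 2 into a single statement, cross-referenced from the other places, that gives:

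- which doses are observed in clinic and which are dispensed;
- the take-home tablet count for each strength;
- who is responsible for the +8 h dose;
- drug days labelled so that they cannot be taken for study days.

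Reconcile the strength in 8.1.6 with Table 1, with components and figures in matching order. Which arrangement and which figures are right is for the sponsor and investigator to decide.

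The cost is protocol wording and a matching dispensing instruction, taken through the amendment approvals in 13.2.2. It needs no additional participants or assays.

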3.3.2 Known Potential Benefits

All volunteers for this study will receive the following benefits for their participation:

- All volunteers will undergo a medical examination at screening free of charge. All volunteers, whether accepted for enrolment into the trial or not, will benefit from this free health check-up. The results of all tests will be communicated to all volunteers. Where illnesses are newly diagnosed, a referral to an appropriate health provider will be made for the volunteer.
- For the short duration of their participation, subjects will receive free health care for acute conditions. In case of chronic conditions, subjects will be referred to appropriate health providers.
- All gametocytic individuals will receive Coartem® and low dose primaquine therapy (excluding pregnant or breast-feeding women for the latter) for the clearance of their malaria infection as the conclusion of their participation in the study. This does not constitute standard of care since asymptomatic individuals do not typically receive malaria treatment. However, clearance of asymptomatic parasitemia is associated with significant health benefits (such as reduction of incidence of chronic anemia and reduction of ongoing malaria transmission).

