9. ASSESSMENT OF SAFETY

9.1 Adverse Events (AE)

Local solicited AEs, as defined in this protocol, include pruritus and erythema at the site of the mosquito bite, in a study participant following DSFA on days 1 and 2. Unsolicited AEs will be captured in study participants after informed consent is obtained and until the subject completes all study procedures.

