9.4 Time Period and Frequency of Event Assessment and Follow-up

The investigator will record all reportable events with start dates occurring any time after informed consent is obtained until the last day of study participation. All AEs not meeting the criteria for severe adverse events (SAEs) will be captured on the appropriate case report form.

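### Optional improvement: non-serious AE capture closes at Day 2 release, before most of the Coartem course, and the safety summaries leave out carriers who are dosed but never fed

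*Protocol*

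**What the plan says.** Participation stops on Day 2, after the second feed and the start of treatment (8.1.5): "Upon release from the clinic, the participation of each subject will be ended". The AE window follows from that. Section 9.1 states: "Unsolicited AEs will be captured in study participants after informed consent is obtained and until the subject completes all study procedures". Section 9.4 records reportable events with onset "any time after informed consent is obtained until the last day of study participation".

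Table 2 in 8.1 has no visit after Day 2. Its AE line, marked for Days 1 and 2, reads "Record local and unsolicited AEs as reported by participant or observed by investigator before DSFA and 30 minutes after DSFA". No AE check is tied to dosing. Section 9.1 names what is solicited after both feeds: "Local solicited AEs, as defined in this protocol, include pruritus and erythema at the site of the mosquito bite".

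On treatment, 3.3.1.5 has participants supervised for the first Coartem dose and then "sent home with the remaining doses and instructions on how to complete the course". Section 7.1.3 adds: "According to standard of care in Kenya for malaria treatment, doses of Coartem on days 2 and 3 will be taken by the subject". Section 8.1.5 instead has treatment day 1 taken after the second feed, with tablets for days 2 and 3 handed over. Of treating these carriers at all, 3.3.2 says: "This does not constitute standard of care since asymptomatic individuals do not typically receive malaria treatment". Sections 7.1.3 and 8.1.6 say that adding primaquine is not standard care in Kenya either.

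Section 8.1.4 offers the same treatment to carriers with a cT of 31 or above, who are not invited to the feeding assays. Section 10.5.1 places all safety assessments in the full analysis population, which 10.4.2 limits to people with at least one skin feed, and counts events from the date of the first feed.

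**The concern.** The study gives two antimalarials to people who would not ordinarily be treated, and stops asking about adverse events when most of the longer course is still to be taken. It also solicits bite-site reactions to two feeds but schedules very different follow-up for each. Finally, its safety denominator is defined by feeding alone, although some people may be dosed without ever being fed.

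At stake is how complete the AE tables are. An SAP could add a table of everyone dosed, but it cannot recover events that nobody collected. The collection window has to be settled in the protocol.

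**Working it through.** No planned figure needs reproducing here. The check is a count of doses, a comparison of observation times and a reading of the population definitions.

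**Doses after release.** Table 1 gives six dosing times: day 1 morning, day 1 at +8 h, and morning and evening on days 2 and 3. At 4 tablets each (the 20/120 mg strength) the course is 6 × 4 = 24 tablets. A footnote sets treatment day 1 as the first day of drug after the second feed, which is study Day 2.

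- Only the first dose in clinic (3.3.1.5, 8.1.6): 6 − 1 = 5 doses after release, 5/6 = 83%, or 5 × 4 = 20 tablets.
- Both day-1 doses in clinic (one reading of 8.1.5): 6 − 2 = 4 doses after release, 4/6 = 67%, or 4 × 4 = 16 tablets.

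The last dose falls on the evening of treatment day 3, which is study Day 4. No section schedules a contact between release and that dose, or after it.

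**Bite-site checks.** The second feed is 24 h ± 3 h after the first, so the Day 2 check before feeding looks at first-feed reactions 21 to 27 h on. The last scheduled check of the second feed is at 0.5 h. Scheduled recording is not the same as time on site. If both day-1 doses are taken in clinic, the second comes 8 h after the first, which itself follows the feed. The person is then on site for 8 h or more after that feed with the AE window still open. If only the first dose is taken there, the protocol fixes no stay beyond 30 minutes.

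**Who enters the safety summaries.**

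- Entry to the full analysis population requires one or more skin feeds (10.4.2).
- All safety assessments use that population, with events counted from the first feed (10.5.1).
- Carriers with cT of 31 or above are offered the drugs but not the feed (8.1.4).
- Anyone in that group who accepts treatment is therefore dosed but cannot appear in the summaries.

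The size of the group depends on how PCR-positive people split at a cT of 31 and on how many accept treatment. The text gives neither.

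**Length of participation.** Day −1 to Day 2 is 4 days, matching the protocol summary. Extending to study Day 4 gives 6 days and to Day 5 gives 7, so two to three days more.

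**The case against.** The strongest reply is that nothing here is wrong. There is no investigational agent and no objective or endpoint concerns safety. Home dosing on days 2 and 3 follows Kenyan practice. The protocol describes Coartem symptoms as generally mild and primaquine effects as mostly transient. Participants receive emergency contacts (13.5.1), unscheduled visits are reimbursed (13.5.2), and 9.5.1 sets no end date for SAE reporting. AEs captured in unfed people would still be listed (10.5) and summarised in continuing-review reports (9.5.1). All of this stands, and it is why the point is optional. It does not close the gap: the passive routes do not extend the non-serious AE window, and listings hold only what was collected.

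Three stronger readings are tempting and unsupported.

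- A reader might infer that the protocol contradicts itself. It does not: participation, AE window and visit schedule end together.
- A reader might infer that second-feed reactions will be under-counted and bias a result. The protocol gives no time course for bite reactions, antihistamine ointment is applied after feeding, time on site may run well past 30 minutes, and no comparison of AEs between feeds is planned.
- A reader might work out the number dosed but unfed by subtracting those fed from the expected PCR-positives among about 400 screened. That assumes every unfed positive has a cT of 31 or above and accepts treatment. Nor can the 36 people with two consecutive feeds stand in for the number fed, because one feed is enough for the safety population.

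People who withdraw add little. Those who leave while under observation have already been fed and are in the safety population.

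**Conclusion.** The point holds as an optional, low-cost improvement. Four or five of six Coartem doses fall after non-serious AE capture has closed, in asymptomatic carriers treated outside standard care. The scheduled check of solicited reactions to the second feed stops at 30 minutes. The safety summaries omit any carrier dosed but never fed.

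The dose count follows directly from Table 1; the one-dose spread comes from the differing accounts of what is taken in clinic. The omission follows from the population definitions, but no head-count can be attached to it. The effect is minor: events between first dose and release are captured, and the primary oocyst analysis does not change.

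**What to change.** - Add one phone or field contact after the last Coartem dose, at about study Day 4 to 5 for fed participants, for each treated and consenting person. Ask about drug reactions and, where the person was fed, bite-site reactions.
- Extend the AE window in 8.1.5, 9.1, 9.4 and Table 2 to that contact, and update the participant duration in the protocol summary.
- In 10.5.1, use a safety set of anyone fed or dosed, counting events from the earlier of first feed or first dose. Summarise drug-related AEs among those dosed and bite-related AEs among those fed, so that each denominator matches its exposure.

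The cost is one contact per treated person, plus CRF and consent wording. Contact details are already held (13.4) and staff already contact participants with PCR results (8.1.4). Recruitment is by homestead visit and telephone access is not documented, so some contacts may need a field visit. Participation lengthens by two to three days. Under 13.2.2 the amendment needs WRAIR IRB and KEMRI SERU approval and the WRAIR Commander's Memorandum, so it is best combined with another amendment if one is planned.
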